### 1.1 Study Hypothesis and Rationale

Bonner *et al* investigated the benefit of the addition of cetuximab to radiation. It was concluded that cetuximab improves locoregional control and reduces mortality without increasing the common toxic effects associated with radiotherapy to the head and neck. In our study, we propose to select locally advanced head and neck cancer patients, who are older than age 70 or are not deemed candidates for chemotherapy. This group was not extensively investigated in the earlier randomized trial, in that

---

 Abbreviations: **CR**, complete response; **EGFR**, epidermal growth factor receptor; **MAPK**, mitogen-activated protein kinase; **PI3K**, phosphatidylinositol 3-kinase; **PR**, partial response; **RT**, radiation treatment/therapy; **STAT**, signal transducer and activator of transcription; **TMA**, tissue microarray.

90% of patients in the Bonner study had a KPS of 80 or greater, and the median age of the patients was 57. The primary end-point of this trial is to characterize local progression free survival in these patients, when treated with cetuximab+radiation.

We also propose to develop a molecular pharmacodynamic predictor of local control after treatment with combination cetuximab-radiation. We hypothesize that tumor EGFR degradation and other markers of down-stream EGFR inhibition as well as novel phosphoproteomic markers observed in tumor biopsies taken 7 days after the administration of cetuximab, will predict the effectiveness of cetuximab-radiation. The first biopsy will be obtained prior to administration of the loading dose of cetuximab. Prior to initiation of cetuximab concurrent with radiation, on Day 7, following the cetuximab loading dose, a tumor biopsy for the biomarkers will be obtained. We hypothesize that tumors that do not demonstrate the changes that correlate with response after cetuximab in the *in vivo* preclinical studies are more likely to progress following cetuximab-radiation therapy compared to those that show changes that correlate with response. If our hypothesis is validated, we will gain a tool that will help identify patients who are most likely to benefit from radiation and cetuximab, a very expensive and moderately toxic treatment.

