## 9.0 Measurement of Response

### 9.4 Tumor Clearance

A primary clinical endpoint of this study is progression-free survival. A patient will be considered to have a complete response if there is no measurable or palpable tumor either on clinical or radiographic (CT-PET scan or MRI) examination assessed within approximately 3 months after the completion of treatment. Complete response will

be defined as complete disappearance of disease (in which case 9.2 will apply to assess relapse) or residual radiographic abnormality (which cannot be safely biopsied) that is not considered to be tumor (in which case section 9.3 will apply to assess progression).

**9.5**                    Local or Regional Relapse

Relapse is defined as reappearance of tumor after complete response. If possible, relapse should be confirmed by biopsy.

**9.6**                    Local or Regional Progression

Progression is defined as an estimated increase in the size of the tumor (product of the perpendicular diameters of the two largest dimensions) of greater than 25%, taking as reference the smallest value of all previous measurements or appearance of new areas of malignant disease.

**9.7**                    Distant Metastasis

Clear evidence of distant metastases (lung, bone, brain, etc.); biopsy is recommended where possible. A solitary, spiculated lung mass/nodule is considered a second primary neoplasm unless proven otherwise.

**9.8**                    Second Primary Neoplasm

Tumor reappearing with the initial and immediate adjoining anatomical region of the primary will be considered local recurrence. Multiple lung nodules/masses are considered distant metastases from the index cancer unless proven otherwise.

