## 21.0 Statistical Considerations

**21.1** General Description: This is a single-arm, Phase II trial to characterize the clinical outcome of standard of care, cetuximab concurrent with radiation, in a special population (head and neck cancer patients who cannot tolerate concurrent chemoradiotherapy due to advanced age, poor performance status or concurrent illness), and to determine if biomarker response to a loading dose of cetuximab is predictive of that outcome.

**21.2** Number of patients: Fifty evaluable patients will be accrued to the trial, which is expected to take 36 months. A patient will be evaluable for the primary objectives if he or she undergoes Research Biopsy #1 and #2 and either completes the full course of cetuximab+RT or has cetuximab+RT stopped for toxicity. Unevaluable patients will be replaced.

**21.3** Analysis plan

**21.3.1 Primary Objective 1:** Determine changes in tumor EGFR, pEGFR, downstream signaling and novel phosphoproteins following a loading dose of cetuximab in patients who are poor candidates for chemoradiation (age  $\geq 70$  years or with significant co-morbidities) and are therefore treated with cetuximab+radiation. These markers will be assessed in tumor biopsies harvested before and after the loading dose of cetuximab. The initial analysis will use descriptive and graphical statistics to determine if any of the markers require transformation prior to analysis. Markers may be assessed on a continuous, ordinal or

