dichotomous scale; markers measured on a continuous scale will be analyzed via general linear models (possibly after transformation), while ordinal and dichotomous markers will be analyzed via cumulative logit and logistic regression analyses, respectively. The primary questions to be answered in this objective are: is the marker modulated by the loading dose of cetuximab; are there baseline clinical or demographic variables that are related to significant variation in biomarker response to the loading dose of cetuximab? For continuous variables, the null hypothesis that the mean value of the change (absolute or percent of baseline) equals zero will be tested by means of a single sample t-test. The second question will be answered by means of analysis of variance on baseline clinical and demographic variables. For dichotomous markers, patients will be stratified into elevated versus not elevated at baseline, and Wald tests on logistic regression parameter estimates will be used to test the null hypothesis that the proportion of patients changing state from baseline is different from 0.5, and to determine if any subset of patients defined by clinical or demographic factors have proportions significantly different from 0.5. Ordinal markers will be handled in a similar fashion.

[figure not shown]
21.3.2 **Primary Objective 2** Characterize clinical outcomes, including local recurrence, progression-free survival and overall survival in these patients, and correlate these clinical outcomes with the changes in tumor EGFR, pEGFR, downstream signaling, and novel phosphoproteins. Logistic regression and proportional hazards (Cox) regression will be used to relate clinical out (local recurrence, progression-free survival or overall survival) to changes in markers across the loading dose. All of the markers will be analyzed, but markers that are modulated by the loading dose (identified in Primary Objective 1) will be of particular interest.

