**21.4 Justification of Design:** While radiation with concurrent cetuximab has become the standard of therapy in patients with locally advanced squamous cell head and neck carcinoma, the clinical outcome of the therapy have not been systematically studied. In addition, therapy with cetuximab is expensive, and, while less toxic than platinum-based therapies, is not without toxicity, and a screen for patients from whom cetuximab would be of benefit would be desirable. Therefore, all patients on this protocol are treated the same, and the primary objectives are focused on comparing patients who do respond to patients who do not. Because this is the standard of care, and these patients have no other treatment options, there is no provision for halting the trial due to low efficacy or excess toxicity (although therapy can, of course, be stopped in individual patients if clinically warranted). The sample size is justified in terms of Primary Objective 2, specifically relating change in a continuous marker to progression-free survival. Monte Carlo simulation was used to simulate the analysis of a single biomarker related to progression-free survival. It was assumed that 50 patients were accrued over 36 months, that the median survival was 22 months, the proportional hazards regression was performed six months after the last patients was treated, and that the biomarker was normally distributed. The power of the null hypothesis of no marker effect (tested at  $\alpha=0.05$ ) was assessed as the effect size of the marker (here, represented as the difference between the mean of the marker for patients with PFS less than the median versus the mean of the marker for patients with PFS greater than the median, divided by the standard deviation) was increased from 0 to 1.5 standard units. The result is shown in Figure 20.1, where it is seen that the power to reject the null hypothesis of no effect is at least 80% if the effect size is 1.1 standard units or greater, which would be considered a moderately large effect.

*Figure 20.1* Power of proportional hazards regression for a marker that discriminates between patients with greater than versus less than median progression-free survival.

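### The 80% power in 21.4 covers one marker on PFS, but 21.3.2 tests all markers against three outcomes with no error control and no exploratory label

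*Combined protocol and SAP*

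**What the plan says.** Section 21.1 gives the trial two purposes. One is to describe outcome; the other is "to determine if biomarker response to a loading dose of cetuximab is predictive of that outcome".

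Section 21.4 bases the sample size on Primary Objective 2: "Monte Carlo simulation was used to simulate the analysis of a single biomarker related to progression-free survival". With 50 patients, alpha 0.05 and a 22-month median, it concludes that "the power to reject the null hypothesis of no effect is at least 80% if the effect size is 1.1 standard units or greater". The effect size is the difference in marker means between patients with PFS below and above the median, "divided by the standard deviation". Which standard deviation is meant, within-group or overall, is not said.

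Section 21.3.2 is the analysis plan for that objective. It uses logistic and Cox regression to relate marker changes to local recurrence, PFS or overall survival. On scope it says "All of the markers will be analyzed, but markers that are modulated by the loading dose" are of special interest. It gives no marker list, primary marker, testing order, adjusted alpha or false-discovery rule. Sections 21.3.3 and 21.3.5 call their own regression models exploratory; 21.3.2 does not.

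The outcome that the marker should predict also varies. Section 1.1 says "The primary end-point of this trial is to characterize local progression free survival in these patients", and then "We also propose to develop a molecular pharmacodynamic predictor of local control after treatment with combination cetuximab-radiation". Section 9.4 says "A primary clinical endpoint of this study is progression-free survival", and 21.4 sizes on PFS.

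**The concern.** The sample size rests on one test of one marker against one outcome. The analysis it supports is a screen of a dozen or so markers against three outcomes, each presumably judged at the same 0.05. Two things follow. A nominally significant marker is a common chance result, and the 80% is not the power of the screen under any rule that controls error.

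This matters because section 1.1 wants a tool to identify who benefits from an expensive and moderately toxic treatment. A chance finding reported under a primary objective, without a label or an error rate, could be taken as that tool.

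**Working it through.** **Inputs**
- From 21.4: 50 patients, 36 months' accrual, analysis six months after the last patient, alpha 0.05, effect size 1.1 SD, and a 22-month median (called survival there; taken as PFS).
- Assumed: exponential PFS, uniform accrual, two-sided testing, and 0.05 per test in 21.3.2, which states no level.

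**1. The plan's own figure.** 21.4 was rebuilt by simulation: a normal marker, shifted by the effect size for patients with PFS below the median, in a one-covariate Cox model with about 25 events. With within-group SD, power is:
- 77-78% at 1.0 SD
- 81-82% at 1.05 SD
- 84-85% at 1.1 SD

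The claim of at least 80% at 1.1 SD is met. If the SD is the overall one, power at 1.1 SD is about 94%; one-sided testing gives about 91%. The claim holds on each reading.

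**2. Number of markers.**
- Section 13.5 names 7: p-EGFR, EGFR, p-ERK1/2, p-AKT, p27, Ki-67, p-STAT3.
- Appendix B (immunoblotting) names 11: phospho and total EGFR, AKT, Src and STAT3 (8), plus p27, PARP and Bcl-XL (3).
- Five are on both lists (p-EGFR, EGFR, p-AKT, p-STAT3, p27), so the union is 7 + 11 - 5 = 13.
- If total AKT, Src and STAT3 only serve as references for their phospho forms, 13 - 3 = 10.
- Both lists are open-ended. Section 1.3 adds EGFR copy number, EGFRvIII and NFκB, giving at most 16 named.

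**3. Chance of a false finding if no marker matters, PFS only.** For m independent tests it is 1 - 0.95^m:
- m = 10: 1 - 0.95^10 = 0.401, with 10 × 0.05 = 0.5 false positives expected
- m = 13: 1 - 0.95^13 = 0.487, with 13 × 0.05 = 0.65 expected

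Running null markers through the same Cox test gives 42% and 51% if independent. At an assumed between-marker correlation of 0.5 it gives 30% and 35%.

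**4. Three outcomes.** Independence gives a ceiling: 1 - 0.95^30 = 0.785 and 1 - 0.95^39 = 0.865. The outcomes overlap, so the true value is lower. With assumed correlations of 0.5-0.8 between outcome statistics and 0-0.5 between markers, it is 49-74% (10 markers) or 56-83% (13).

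**5. Power under an error rule.** Benjamini-Hochberg at 10% rejects the k smallest p-values, where k is the largest rank with p(k) ≤ k × 0.10/m. A marker significant on its own must reach 0.10/13 = 0.0077 with 13 markers, or 0.10/4 = 0.025 with four. Per-marker power at 1.1 SD, within-group SD:

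| List | True markers | Power |
|---|---|---|
| 13 | 1 | about 60% |
| 13 | 3 | about 73% |
| 13 | 5 | about 78% |
| 4 | 1 | about 77% |

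With one true marker of 13, 80% power needs about 1.35 SD.

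**6. What the rule buys.** With one true marker of 13 at 1.1 SD and null-marker correlation 0-0.5, at least one false marker is also significant in 34-48% of trials at plain 0.05, against 12-16% under Benjamini-Hochberg. The false discovery rate is 22-29% against 8-10%.

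**The case against.** The best defence is that nothing in 21.4 is false. It says openly that one biomarker was simulated, and it never claims 80% for a screen. That stands. A reader might infer that the power calculation is wrong or the trial too small; the documents do not support this, since the figure reproduces for what it describes.

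Second, Objective 2 speaks of characterising and correlating, and section 1.1 of developing a predictor, in a single-arm Phase II trial. The exploratory labels in 21.3.3 and 21.3.5 are justified there by sparse data, not multiplicity, so the contrast with 21.3.2 is weaker than it looks. This partly stands: labelling all of 21.3.2 exploratory would meet much of the concern. But the objective is primary, it sets the sample size, and 21.1 gives it a yes-or-no question.

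Third, the count of 13 is assembled from two laboratory lists, and one true marker of 13 is the least favourable case for Benjamini-Hochberg. This stands too. The markers belong to linked EGFR signalling, so several could be true together. With 13 markers and correlation 0-0.5, the chance of finding at least one true marker is 77-85% if two are true, 86-95% if three and 93-99% if five. A reader might take 60% as the power of the screen; the documents do not fix the number of true markers, so only a range is defensible.

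The special interest in modulated markers does not help: it sets emphasis, and all markers are still tested.

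**Conclusion.** The concern holds in this form: the 80% power at 1.1 SD is correct for one pre-named marker on PFS at unadjusted alpha 0.05, and it does not describe the screen in 21.3.2. If no marker matters, that screen yields at least one p<0.05 on PFS alone in about 40-49% of trials with independent markers, and about 30-35% at correlation 0.5; adding outcomes raises this. The correlations are assumed, and 0.05 per test is carried over from 21.4.

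A reader might also infer that analysing change without baseline biases these models. The documents do not establish it: section 1.2 links EGFR expression to poor prognosis, while 1.3 reports that pretreatment EGFR failed to predict response. Nor do they give the inputs needed to size an effect, or to recompute power for local progression-free survival. Neither is part of this point.

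**What to change.** **In 21.3.2:**
- Name a closed list of primary marker changes: the full 10-13, or a shorter list such as the changes in total EGFR, pEGFR, pSTAT3 and Bcl-XL from section 1.3.
- Fix one scale of change; 21.3.1 allows absolute or percent.
- Name PFS, the sizing endpoint, as the single outcome for the screen, and reconcile section 1.1 with 9.4 and 21.4.
- Control the false discovery rate across the list by Benjamini-Hochberg, for example at 10%.
- Label all other markers, novel proteins and outcomes exploratory.

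**In 21.4:**
- State that 80% at 1.1 SD applies to one pre-named marker at unadjusted alpha 0.05.
- Say whether the SD is within-group or overall.
- Give power under the chosen rule as a range over list size and number of true markers, as in the table above.

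A sensitivity analysis adjusting for the marker's baseline level is optional.

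**Cost:** wording only, with no added patients or biopsies. The downside is a less favourable stated power, such as 1.35 SD instead of 1.1 SD for 80% when one of 13 markers is true. A shorter list softens this, but moves some markers to exploratory status.

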In the Bonner trial and in the Vermorken study there was an increased survival benefit that was associated with oropharynx sites. High risk HPV (human papilloma virus) infection has been implicated both as an etiologic factor and as a prognostic factor for survival and response to therapy. HPV is also typically associated with a younger cohort of patients, however as the high risk HPV infected cohort ages, we do expect to see more patients in their 70s and beyond who will have HPV-related head and neck cancers. Thus, we postulate the EGFR inhibition will work better in HPV positive tumors. We will investigate the presence of HPV in the tumor tissue biopsies by a variety of assays. We will also examine the p53 status using RNA isolated from the tumor biopsy since HPV positive tumors most frequently have wild type p53 which may also contribute to the high response rate of these tumors.

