### 2.2 Secondary

- 2.2.1 Conduct normal mucosa EGFR assessment for comparison with tumor sample.
- 2.2.2 Correlate HPV presence and titer with p53 status and clinical outcome.

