### 7.2 Research Component (Treatment with cetuximab and associated biopsies)

All patients will sign an informed consent for clinical and research biopsies. All biopsies will be performed by an otolaryngologist or oral surgeon who is a co-investigator of the study. The proposed tissue accrual should be adequate for all of the proposed studies.

- 7.2.1 Research Biopsy #1: Patients will be consented and enrolled in this study prior to this biopsy. The biopsy will be performed no more than 4 weeks prior to the loading dose of cetuximab. It will be performed under local anesthesia (in the event a patient requires further clinical staging or confirmation of diagnosis under general anesthesia, the research biopsy may be performed at that time.) This pre-treatment biopsy will be performed for research purposes if a suitable clinical biopsy specimen is not available. A clinical specimen will be suitable if the biopsy was performed within 4 weeks of the loading dose of Cetuximab.
- 7.2.2 Research Biopsy #2: This will be done 7 days (+/- 1 day) after the cetuximab loading dose (Day 0).
- 7.2.3 Normal Oral Mucosa Sampling: Baseline EGFR of the normal oral mucosa will be obtained by buccal swab or normal mucosa biopsy. If using buccal swabs, at least 3 normal oral mucosa buccal swab

samples will be acquired. This sampling will occur at both Research Biopsy #1 and Research Biopsy #2.

**7.3 Cetuximab/Radiation Schedule:** Cetuximab will be delivered as standard of care per the package insert.

- 7.3.1 Day 0: Patients will receive a single dose of cetuximab 400 mg/m^2.
- 7.3.2 Day 7 (+/- 1 day): Biopsy #2 will be obtained
- 7.3.3 Following the biopsy, within approximately 4 days, daily radiation therapy with weekly cetuximab will be initiated.
- 7.3.4 Patients will receive weekly cetuximab 250 mg/m^2. On days of radiation therapy and cetuximab administration, cetuximab will be given prior to radiation therapy.

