#### 13.5

##### Method of Assessment of EGFR Expression in Tumor After Cetuximab

##### Loading Dose

At the time of the second biopsy, four core biopsies from different areas of the tumor as well as swab of the normal appearing mucosa will be obtained. Four core biopsies will be processed with one core used in high-throughput immunoblot analysis, one core will be fixed in formalin to be embedded in paraffin, one core will be frozen and fixed in Tissue-Tek OCT for immunofluorescence analysis and one core will be used for RNA and DNA isolation using Trizol. EGFR phosphorylation analysis using immunoblotting and immunohistochemistry will be performed in the surgical specimen and immunofluorescence analysis will also be performed if sufficient tissue is available using standard methods. Interpretations of the staining will be performed according to the standard guidelines. The EGFR and critical associated down-stream signaling pathways will be analyzed post- induction therapy, including p-EGFR and total EGFR, p-ERK1/2, p-AKT, p27, Ki-67, and p-STAT3, and other markers that we may discover in our preclinical studies. EGFRvIII expression and p53 mutation analysis will be assessed on cDNA obtained from total RNA converted with RT-PCR. Genomic DNA from the tumor biopsy will be used to test for HPV presence and type as carried out by PCR-mass spect using the AttoSense assay at SensiGen, LLC.

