21.3.3 **Primary Objective 3** *Describe the toxicity, in particular mucositis/dysphagia, of this regimen.* Adverse events will be tabulated by grade (NCI CTCAE v4), category (mucositis and dysphagia are expected to be the most common) and relatedness to treatment (not, unlikely, possibly, probably or definitely). The proportion of patients experiencing Grade 3 or worse adverse events at least possibly related to treatment will be calculated, accompanied by a 95% exact binomial confidence interval. Possible baseline demographic and clinical predictors of such toxicity may be evaluated by means of logistic regression, but, due to the low expected number of such toxicities, any such modeling will be strictly exploratory.

21.3.4 **Secondary Objective 1** *Conduct normal mucosa EGFR assessment for comparison with tumor sample.* The change in tumor EGFR level across treatment, relative to EGFR in normal mucosa, will be evaluated by means of repeated measures ANOVA.

21.3.5 **Secondary Objective 2** *Correlate HPV presence and titer with p53 status and clinical outcome.* HPV status ( $\pm$ ) will be added to the models of Primary Objective 2 to determine if +HPV patients respond to therapy differently than -HPV patients, but, due to the limited expected number of +HPV patients, such analyses will be considered exploratory.

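### Section 21.3.5 estimates the HPV effect only with the Day 7 marker change in the model, so it omits whatever part of that effect runs through the marker and does not give the overall HPV difference

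*Combined protocol and SAP*

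**What the plan says.** Objective 2.2.2 is to "Correlate HPV presence and titer with p53 status and clinical outcome". Section 21.3.5 repeats it and gives one analysis: HPV status, coded positive or negative, "will be added to the models of Primary Objective 2 to determine if +HPV patients respond to therapy differently than -HPV patients". It labels this exploratory because few HPV-positive patients are expected.

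The Primary Objective 2 models are defined in section 21.3.2. Logistic and Cox regression relate local recurrence, PFS or OS "to changes in markers across the loading dose". The second biopsy that supplies the change is taken on Day 7 (plus or minus one day) after the cetuximab loading dose (section 7.2.2). Section 21 describes no HPV model without a marker.

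Section 1.1 gives the reasoning on HPV: "we postulate the EGFR inhibition will work better in HPV positive tumors". It also calls HPV a prognostic factor in general, and adds that "HPV positive tumors most frequently have wild type p53 which may also contribute to the high response rate of these tumors".

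On measurement, section 13.5 says tumour DNA will be used to "test for HPV presence and type as carried out by PCR-mass spect using the AttoSense assay", and p53 mutation is assessed on cDNA. Section 21 contains no analysis of p53 or of titer beyond restating the objective.

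**The concern.** Whether HPV-positive patients respond differently is a question about the overall difference between two groups defined before treatment. The planned coefficient answers a narrower one: how the groups differ among patients with the same Day 7 marker change. If HPV-positive tumours do better partly because cetuximab inhibits EGFR signalling more in them, that part of the difference sits in the marker term and leaves the HPV term. What remains is a direct effect, and only if nothing else drives both marker change and outcome.

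There is also no single answer. Section 21.3.2 says every marker will be analysed. Section 13.5 names seven (total EGFR, p-EGFR, p-ERK1/2, p-AKT, p27, Ki-67, p-STAT3), besides any found later. Fitted one at a time, as in the simulation in section 21.4, these give 7 × 3 outcomes = 21 HPV coefficients. Each removes a different share of the effect, and none is named as the result. A reader of the final report could take a ratio pulled toward 1 as the overall HPV effect.

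A smaller gap is that the HPV–p53 part of objective 2.2.2 has no planned analysis, although both are to be measured.

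**Working it through.** **The plan's own figure.** The plan gives no figure for HPV. Its only power statement (section 21.4) concerns a single marker: at least 80% at 1.1 standard units, with 50 patients accrued over 36 months, median 22 months, analysis six months after the last patient, and α = 0.05 (two-sided assumed).

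Expected events, with exponential PFS and uniform accrual:
- λ = ln 2 / 22 = 0.0315 per month; follow-up is uniform on 6 to 42 months.
- P(event) = 1 − [exp(−6λ) − exp(−42λ)] / (36λ) = 1 − (0.828 − 0.266) / 1.134 = 0.505.
- Events = 50 × 0.505 = 25.2.

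Simulated Cox power at 1.1 is 84–85% if the standard deviation is within group and about 94% if it is overall. The stated lower bound reproduces, so the same time frame is used below.

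**HPV model.** Assumptions, none given by the documents: total HPV log hazard ratio ln 0.4 = −0.916; HPV prevalence 10%, 20% or 30% (5, 10 or 15 of 50 patients); marker change M one SD higher in HPV-positive tumours; a share s of the HPV effect carried by M.
- M = HPV + N(0,1)
- hazard = λ exp(b·M + c·HPV), with b = s·ln 0.4 and c = (1 − s)·ln 0.4
- With M in the model, the HPV hazard ratio is exp(c) = 0.4^(1−s).

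Median estimates at N = 50 and 20% HPV-positive (1,500 runs; runs with an HPV standard error above 3 dropped, leaving 1,415 to 1,442):

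| Share via marker | 0.4^(1−s) | HPV alone | HPV plus marker | Power, HPV alone | Power, HPV plus marker |
|---|---|---|---|---|---|
| 0% | 0.40 | 0.42 | 0.41 | 18% | 17.5% |
| 25% | 0.50 | 0.41 | 0.50 | 20% | 9% |
| 50% | 0.63 | 0.42 | 0.65 | 17% | 4% |
| 75% | 0.80 | 0.46 | 0.82 | 15% | 2% |
| 100% | 1.00 | 0.47 | 1.03 | 14% | 5% |

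With 5,000 patients the pairs are 0.40 and 0.40 (0%), 0.42 and 0.62 (50%), and 0.48 and 1.00 (100%). The HPV-alone ratio drifts from 0.40 to 0.48 because hazard ratios are non-collapsible when a prognostic marker is left out. That drift is small beside the shift from adjustment.

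**Precision.** At 30% HPV-positive, simulated power with HPV alone is 27–39%; at 10% both models are below 8%, with about a quarter of runs dropped. A normal approximation on 25 events, Φ(√(25·p(1−p))·0.916 − 1.96), gives 28%, 45% and 56% at p = 0.1, 0.2 and 0.3. It is optimistic because, at a ratio of 0.4, HPV-positive patients supply fewer events than their share of the sample.

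**Imperfect marker.** Appendix B scores staining from 1 to 4 and calls immunofluorescence semi-quantitative, so M carries measurement error. In a separate setup (0.8 log hazard ratio per SD, full mediation, 20% HPV-positive, about 0.5 unadjusted), the adjusted ratio is about 0.88, 0.75 and 0.67 at assumed reliabilities of 0.8, 0.6 and 0.5.

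**The case against.** Four points can be made for the plan.

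First, a reader might infer that the HPV effect is adjusted away entirely. The documents do not support that. Section 1.1 names two further routes, wild-type p53 and general prognosis, which could bypass EGFR marker change and stay in the HPV coefficient. Measurement error also leaves part of a mediated effect there. This stands.

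Second, a reader might infer that marker change has no place in a model with HPV. That is also too strong. HPV status precedes the Day 7 biopsy and may confound the marker–outcome relation that the trial is built to study, so adjusting the marker effect for HPV is legitimate. The postulate could also mean effect modification, which needs both terms; section 21.3.5 does not say whether HPV enters as a main effect or an interaction. This stands too, but neither use yields the overall HPV difference.

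Third, the analysis is secondary, labelled exploratory and weakly powered under any model. That limits the consequence. It does not decide which quantity to estimate, and in an exploratory analysis the estimate and its interval are the whole product.

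Fourth, section 1.1 promises several HPV assays, so a quantitative readout may be intended even though section 13.5 names only presence and type. Replacing titer by type would swap one quantity for another. That stands; the gap is that no readout is named.

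**Conclusion.** The concern holds in a limited form. As written, the plan estimates HPV only conditional on a post-cetuximab variable that section 1.1 places on one postulated HPV route. The coefficient omits the share carried by that marker, varies across marker models, and does not answer the question that section 21.3.5 sets. A marker-free model is the better method for that question.

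The size cannot be fixed from the documents. Under the assumptions above it runs from no loss at 0% mediation, through 0.42 becoming about 0.65 at 50%, to about 1.0 only at 100% mediation with an error-free marker. It does not follow that the trial would report HPV as irrelevant: an imprecise exploratory ratio near 1 would not justify that claim, and the HPV-only model would itself usually be non-significant.

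The marker-free estimate has its own limit. In a single-arm trial it describes the HPV difference under this treatment and cannot separate general prognosis from better response to EGFR inhibition.

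The missing p53 and titer analyses are a minor gap of detail.

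**What to change.** In section 21.3.5:

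1. Fit local recurrence, PFS and OS on HPV status with no Day 7 marker in the model, using the model types of section 21.3.2. Report the resulting odds or hazard ratio with its 95% CI as the answer to Secondary Objective 2.
2. Keep the marker-plus-HPV model, stated as a separate question: the marker effect adjusted for HPV, or mediation. Say whether HPV enters as a main effect or as an interaction.
3. Keep the exploratory label.
4. Minor: add the HPV by p53 (wild type or mutant) cross-tabulation with an odds ratio and exact CI. Either name the quantitative HPV readout and how it will be analysed, or remove titer from 2.2.2 and from the restated objective in 21.3.5.

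The cost is SAP wording, three extra model fits and one table on data already planned. It needs no extra patients, biopsies or visits. An additional assay would be needed only if titer is kept and no planned assay measures it.
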